To further illustrate the point concerning the impact of foot ulcers: the healing rate of DFUs is poor; on average, 24% of wounds have healed by week 12 of treatment, and only 31% at 20 weeks of treatment (Margolis, 1999). A cohort study involving 31 diabetic patients determined that the average healing time for neuropathic DFUs is 78 days whereas this increases to 133 days for patients with additional peripheral vascular disease (Zimny et al, 2002). Further analysis has shown that the size of the ulcer negatively correlates to the healing rate, whereas a patient's age, sex, or type of diabetes is not associated with a change in healing rate outcome (Oyibo, 2001). DFU healing progress at 4 weeks of treatment is a predictor of the likelihood that the wound will be healed by 12 weeks of treatment. If the wound has not healed by at least 50% after 4 weeks, the likelihood that the DFU will be completely healed by 12 weeks is reduced to circa 10% (Sheehan, 2003). Taken together, there is a major group of patients with DFU -those with larger ulcers, and co-morbidities, responding poorly to standard treatment in the first 4 weeks – that is at risk of ending up with long-term wounds taking over 3 months to heal, if at all.

Oxygen is an essential component of the wound healing process (Hunt et al, 1969). Poor circulation due to diabetic angiopathy impairs the healing process and limits the degree of required growth factor release and angiogenesis (Falanga, 2005; Mathieu et al, 2006). Increasing oxygen levels can be achieved in various ways, including hyperbaric chamber treatment (Faglia, 1996). However, this method is costly, cumbersome and logistically challenging. A novel haemoglobin spray that is designed to enhance wound healing, including non-diabetic foot ulcers and DFUs, by enriching the wound area with oxygen using porcine haemoglobin is now available in the UK. The product is called Granulox and it marketed by InFirst Healthcare Ltd. The mode of action is the application of porcine haemoglobin onto a wound to facilitate increase oxygen levels through diffusion into the wound area (Arenberger et al, 2011; Norris, 2014; Hunt & Elg, 2016). Hunt & Elg, in a study with retrospective analysis of standard care DFUs and prospective assessment of Granulox adjunct therapy DFUs, have shown that the healing rate for chronic wounds is much accelerated with haemoglobin treatment. Figure 1 summarises their data.

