6. SUBJECTS

6.1 Anticipated number of research subjects

There is pilot data to base a *priori* sample size calculation on, but this concerns a single retrospective study (Hunt and Elg, 2016). In their study, they observed 37% (control) and 89% (Granulox) wound size change versus baseline measurement at 12 weeks. This would mean that 14 patients (7 in each arm) would be sufficient to have the trial powered to 80%. For this present trial, a more conservative approach is taken, see Table 4. The earlier published average healing rate of 25% is used as the anticipated minimum healing rate (Margolis, 1999). Since some patients may require surgical intervention or may withdraw, a hypothetical 20% dropout rate is calculated into the sample size (actual attrition rate is a study objective). A theoretical 1:1 allocation to the control and Granulox intervention group respectively will be applied. However, because the PUSH score is not known beforehand this may not be achieved if more patients are recruited into one of the two PUSH cohorts. Diabetic foot ulcers (DFUs) and other foot ulcers will be randomised from separate randomisation lists.

The primary outcome, average percentage decrease in ulcer size between baseline and 12 week follow-up is used for sample size calculation. Power calculations for sample size, 80% power and 5% significance, based on two-sided Mann-Whitney U-test. A priori power calculations using GPower 3.1 software, result in the following sample size summarized in Table 4. This is based on the DFU study by Hunt and Elg. A further 20 patients with non-diabetic foot ulcers will be recruited to pilot what impact Granulox has on those types of wounds.

Table 4, Sample size calculation

	Median change in DFU ulcer size at 12 weeks (presume decrease for both arms, ie one-tailed approach)	Standard Deviation
Arm A (hypothetical)	52%	30%
Arm B (hypothetical)	25%	30%
	Power beta of 80%, Alpha p-value of Sample size required without any dro	

Sample size with 20% attrition rate included: 40

Total of 40 DFU patients:

- 20 Patients to receive treatment as usual (TaU)
- 20 Patient to receive TaU plus Granulox spray

Plus 20 non-DFU foot ulcers:

- 10 Patients to receive treatment as usual (TaU)
- 10 Patient to receive TaU plus Granulox spray

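### Table 4's control mean of 25% and SD of 30% cannot both hold with the 24% closure the protocol cites, so the 80% power for 40 DFU patients is not supported

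*Protocol*

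**What the plan says.** Section 6.1 of the protocol defines the sizing quantity as a mean: "The primary outcome, average percentage decrease in ulcer size between baseline and 12 week follow-up is used for sample size calculation". The heading of Table 4 calls it a median and adds a one-tailed remark: "Median change in DFU ulcer size at 12 weeks (presume decrease for both arms, ie one-tailed approach". Table 4 sets 52% in Arm A and 25% in Arm B, each with an SD of 30%, and marks both arms as hypothetical. I read Arm A as Granulox and Arm B as control.

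The control value is explained this way: "The earlier published average healing rate of 25% is used as the anticipated minimum healing rate". The source cited there is the meta-analysis of standard care that section 2 (Introduction) summarises as "on average, 24% of wounds have healed by week 12 of treatment, and only 31% at 20 weeks of treatment". So the cited 24% is a proportion of wounds closed.

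No SD is quoted from any source. The calculation as a whole is attributed to the retrospective pilot DFU study (37% versus 89%, for which 7 per arm is said to suffice). The test is described as "Power calculations for sample size, 80% power and 5% significance, based on two-sided Mann-Whitney U-test". The result is 40 DFU patients, including 20% attrition.

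**The concern.** Percentage decrease in area cannot exceed 100%, and every healed ulcer sits exactly at 100%. A sizeable healed share therefore sets a lower limit on the SD once the mean or median is fixed. If about a quarter of controls are at 100% while the control average is 25%, the spread must be large, and 30 points looks too small.

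The standardised effect is 27/30 = 0.9, and the 40 DFU patients follow directly from it. If the SD is too small for the assumed mean and closure share, the printed power has no consistent basis. A null result could then be read as evidence against an effect that the trial may have had a poor chance of detecting.

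**Working it through.** **Inputs.** Means or medians of 52% and 25%, SD 30%, 5% significance, 80% power, 20% attrition (section 6.1 and Table 4). Closure of 24% by week 12 for DFUs in general, and circa 10% for ulcers less than 50% healed at 4 weeks (section 2). Only ulcers healed less than 50% over the two-week run-in are randomised (section 6.1.1).

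**1. The plan's figure.** d = (52 − 25)/30 = 0.90. At one-sided 5% and 80% power, a t-test needs 16 per arm; 32/0.8 = 40, as printed. With the Mann-Whitney efficiency for a normal parent (3/π) it needs 17 per arm. Two-sided, 21 to 22 per arm are needed, or 53 to 55 in total with attrition, which is not 40. Sidedness is a separate issue, so both tails are shown below.

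**2. Possible origin of the SD.** With the pilot difference of 89 − 37 = 52 points and SD 30, the two-sided calculation gives exactly 7 per arm. The 30 may therefore have come from the pilot-based calculation, but the protocol does not say so.

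**3. Minimum SD if 25% is a mean.** With a share p at 100 and overall mean μ, the SD is smallest when all unhealed ulcers have the same value: SD ≥ (100 − μ) × √(p/(1 − p)).
- p = 0.24: 75 × √(0.24/0.76) = 42.1. The unhealed ulcers would average (25 − 24)/0.76 = 1.3%.
- p = 0.10: 75 × √(0.10/0.90) = 25.0.
- SD 30 requires p/(1 − p) ≤ (30/75)² = 0.16, so p ≤ 0.16/1.16 = 13.8%.
- Conversely, with p = 0.24, SD 30 requires a mean of at least 100 − 30/√(0.24/0.76) = 46.6%.

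**4. Minimum SD if 25% is a median.** Only half the patients need be at or below 25. The minimum has 50% at 25, 24% at 100 and the remaining 26% at the overall mean, (0.50 × 25 + 0.24 × 100)/0.74 = 49.3. Then SD = √(0.50 × 24.3² + 0.24 × 50.7²) = 30.2. With p = 0.10 the same construction gives 21.7. For a smoother shape (24% healed, overall median 25, normal unhealed changes capped below 100), unhealed SDs of 10, 20 and 30 give total SDs of about 35, 40 and 46.

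**5. Normal-theory Mann-Whitney power** (27-point difference, same SD in both arms, noncentral t with efficiency 3/π):

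| SD | Per arm | One-sided | Two-sided |
|---|---|---|---|
| 30 | 16 | 78% | 67% |
| 30 | 20 | 86% | 77% |
| 42.1 | 16 | 53% | 40% |
| 42.1 | 20 | 62% | 49% |

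Sixteen per arm is 40 × 0.8/2; twenty assumes no attrition. A normal distribution with mean 25 and SD 30 puts only 0.6% of controls at or above 100.

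**6. Simulated Mann-Whitney power with a point mass at 100** (16 per arm, means 25 and 52, same closure share in both arms; the closure share on Granulox and the unhealed SDs are assumptions):
- 24% healed: two-sided power about 80% with unhealed SD 10, 62% with SD 20 and 41% with SD 30.
- 10% healed, unhealed SD 20 (control SD about 31): about 83% two-sided and 90% one-sided.

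Repeat runs move these figures by a point or two.

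**The case against.** A reader might infer that an SD of 30% is arithmetically impossible however Table 4 is read, and that power is therefore below 80% on either tail. The documents support neither inference.

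- **Median reading.** The minimum is 30.2, which rounds to the printed 30. That distribution is artificial, so 30 is implausible on this reading, but not impossible.
- **The 24% is not this trial's closure rate.** It describes DFUs in general. The run-in removes fast healers, and the protocol itself cites circa 10% closure for slow responders, at which SD 30 is feasible on both readings.
- **Power does not follow from the SD alone.** The Mann-Whitney test depends on the shape of the distributions. With tightly clustered unhealed ulcers it reaches 80% or more even with 24% healed, and nothing in the protocol fixes that spread.
- **The SD may not be the faulty input.** With 24% closed, SD 30 becomes feasible once the control mean is at least 46.6%. The 25% looks like a closure proportion reused as a mean area reduction.
- **The SD is not wholly without a basis.** The calculation is attributed to the pilot study, 30 reproduces the 7 per arm, and both arms are labelled hypothetical.

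All five points stand, and they limit the conclusion. They do not remove the conflict on the endpoint as the text words it, nor supply the missing statement of what 25% is.

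**Conclusion.** The point holds in a conditional form. Taken as the average that section 6.1 names, a control value of 25%, closure of 24% and an SD of 30% cannot all be true: the SD would have to be at least 42.1, or closure at most about 13.8%. The protocol does not settle whether 25% is a mean or a median, gives no closure share for the population left after the run-in, and does not say where the SD comes from.

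The 80% power is therefore unsupported, rather than shown to be wrong by a fixed amount. On normal theory with 16 evaluable per arm, moving from SD 30 to SD 42 takes power from 78% to 53% one-sided and from 67% to 40% two-sided. With healed ulcers at 100%, two-sided power runs from about 41% to about 83% over the cases in step 6, depending on a closure share (10 to 24%) and an unhealed spread that are both assumptions. Lower power than printed is likely, not certain.

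**What to change.** Keep the sample size at 40 DFU patients and revise section 6.1 and Table 4 as follows:

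1. State whether 25% and 52% are means or medians of percentage area reduction, use the same term in text and table, and make clear that 25% is not a closure proportion. If it was taken from one, replace it with an area-reduction figure.
2. State the control closure share assumed after the run-in, for example a range of 10 to 24%.
3. Give the source of the SD, and use a value compatible with both the centre and the closure share.
4. Recompute power for the stated two-sided Mann-Whitney test by simulation, with a point mass at 100% for healed ulcers and a stated range for the spread of unhealed ones.
5. Replace the single 80% with the resulting range and its assumptions.

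The cost is a short recalculation and a wording change, with no extra patients. The drawback is that the printed power will probably be less favourable.

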The CONSORT guidelines require a statement on the number of patients assessed for eligibility (Schulz, Altman & Moher 2010). The number of patients screened but who did not meet the inclusion criteria or who declined to participate will be recorded, as will any patients who are lost to follow-up (Appendix 3).

The calculation does take into account a 10% patient attrition rate (withdrawal and loss to follow-up), since this involves a study with at least two visits. Patients will be recruited from the adult (age 18+) population routinely seen by the evaluating clinical staff members.

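### Section 6.1 gives two attrition rates, 20% and 10%, for the one sample-size calculation behind the 40 diabetic foot ulcer patients

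*Protocol*

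**What the plan says.** All of the relevant text is in Protocol section 6.1.

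- **Attrition, opening paragraph.** Because some patients may need surgery or may withdraw, "a hypothetical 20% dropout rate is calculated into the sample size". The paragraph adds that the attrition actually observed is an objective of the study.
- **Attrition, below Table 4.** "Sample size with 20% attrition rate included: 40", which is then split into 20 DFU patients per arm.
- **Attrition, last paragraph before section 6.1.1.** "The calculation does take into account a 10% patient attrition rate (withdrawal and loss to follow-up"; the reason given is that the study involves two or more visits.
- **Test and error rates.** "Power calculations for sample size, 80% power and 5% significance, based on two-sided Mann-Whitney U-test". The column heading of Table 4 says instead "presume decrease for both arms, ie one-tailed approach".
- **Effect.** "Arm A (hypothetical) 52% 30" and "Arm B (hypothetical) 25% 30", both in percent.
- **Allocation.** "A theoretical 1:1 allocation to the control and Granulox intervention group respectively will be applied".

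The 20 patients with non-diabetic ulcers are added as a pilot, with no calculation of their own.

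**The concern.** The attrition rate decides how many week-12 ulcer measurements the power claim rests on. Section 6.1 gives two rates and presents only one calculation that includes attrition, so both must describe the same step. The 10% cannot belong to the non-diabetic patients, because no calculation is given for them.

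At stake are the number of evaluable DFU patients the primary comparison was planned on and the power quoted for it. There is also a reporting problem. Observed attrition is to be reported as a result, and a loss of, say, 15% would be within one stated assumption and beyond the other.

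**Working it through.** **Inputs (section 6.1 and Table 4).** Changes of 52% and 25%, SD 30% in each arm, 1:1 allocation, alpha 5%, power 80%. Standardised difference d = (52 − 25)/30 = 0.90.

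**Step 1: reproduce the printed 40.** The power of a one-tailed t-test with n per arm is P(T > t(0.95; 2n − 2)), where T is noncentral t with 2n − 2 degrees of freedom and noncentrality d·√(n/2). At n = 16 the noncentrality is 0.90 × √8 = 2.55 and the power is 80.0%. That gives N = 32 before attrition, and 32/(1 − 0.20) = 40, the printed figure. The same 32 at 10% gives 32/0.90 = 35.6, rounded up to 36.

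**Step 2: try other routes.** For the Mann-Whitney test, n is multiplied by the asymptotic relative efficiency under normality, 3/π = 0.955.

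| Method | N before attrition | N at 20% loss | N at 10% loss |
|---|---|---|---|
| One-tailed t-test | 32 | 40 | 36 |
| One-tailed Mann-Whitney | 34 | 43 | 38 |
| Two-sided t-test | 42 | 53 | 47 |
| Two-sided Mann-Whitney | 44 | 55 | 49 |

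Two further routes also reach 40. A pre-attrition N of 36 at 10% gives 36/0.90 = 40, and a two-sided normal approximation needs 20 per arm with no allowance for loss. The cell of Table 4 that would settle the matter is cut off in the text read here.

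**Step 3: evaluable patients out of 40.** At 20% loss, 40 × 0.80 = 32 (16 per arm). At 10% loss, 40 × 0.90 = 36 (18 per arm). These two numbers do not depend on how 40 was obtained.

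**Step 4: Mann-Whitney power at those numbers (d = 0.90, alpha 5%).** The effective n per arm is 16 × 0.955 = 15.3 (noncentrality 2.49) or 18 × 0.955 = 17.2 (noncentrality 2.64).

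| | 16 per arm (20% loss) | 18 per arm (10% loss) | Gap |
|---|---|---|---|
| One-sided | 78.3% | 82.6% | 4.3 points |
| Two-sided | 67.1% | 72.6% | 5.5 points |

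A simulation with normal data (20,000 replicates) gives 76.9% and 82.4% one-sided, and 65.5% and 72.0% two-sided. Those powers are slightly lower and the gaps slightly wider, at about 5.5 and 6.5 points.

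**Step 5: separate the attrition effect from the sidedness effect.** With no loss at all (20 per arm), two-sided Mann-Whitney power is 77.2% by the same approximation. The two-sided test therefore misses 80% whichever attrition rate is used.

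**The case against.** **The consequence is small.** N, allocation, the primary test and trial conduct are the same under either rate. The 20% is stated twice, once beside N itself, so a careful reader is unlikely to plan on 10%. It is called hypothetical, and no rule in the protocol depends on it. All of this stands and limits the weight of the point. It does not remove the contradiction.

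**The two sentences describe different losses.** The 20% is linked to surgery or withdrawal, the 10% to withdrawal and loss to follow-up. The lists overlap without being identical. Both rates, however, are said to be built into the sample size, and nothing shows them being combined or applied to different steps.

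**Stronger readings that the protocol does not support:**

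- A reader might infer that only 20% can produce 40. This is not shown. The pre-attrition number is not legible, 36/0.90 is also 40, and the named Mann-Whitney test run one-tailed needs 34, which becomes 43 after 20% loss. The case for 20% rests first on the protocol's own label; the exact match at 32/0.80 is supporting evidence.
- A reader might take the reference to two or more visits as proof that the 10% sentence was not written for this trial. The phrase is generic, but it is true of a schedule with visits at weeks −2, 0, 3, 6, 9 and 12.
- A reader might blame the two-sided powers of 67% and 73% on the attrition conflict. They come mainly from the separate conflict between a two-sided test in the text and a one-tailed approach in Table 4. Attrition accounts only for the gap between them.

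**Conclusion.** The contradiction is real and lies within section 6.1. As written, the 10% sentence disagrees with the rate the protocol itself attaches to N = 40. The two rates imply 32 or 36 evaluable DFU patients, worth about 4 to 6 points of Mann-Whitney power: 78% against 83% one-sided, 67% against 73% two-sided.

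The evaluable numbers are plain arithmetic on 40. The power figures assume Table 4's effect and SD, roughly normal percentage changes, equal arms and loss spread evenly across arms. The pre-attrition 32 is a reconstruction that assumes a one-tailed t-test, and the authors must confirm it.

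At the 32 patients that the labelled 20% leaves, the named test does not reach the stated 80% under either sidedness, though it comes close one-sided. This is a correction to the stated basis of the power claim; it gives no reason to change the sample size.

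**What to change.** In section 6.1:

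1. Delete the 10% sentence or correct it to 20%, so that a single planning rate stands and serves as the reference for observed attrition.
2. Confirm the pre-attrition N from the authors' own Table 4 and state it in the text with the test and sidedness used. If it is not 32, explain how it leads to 40 at 20% loss.
3. Restate the power of the named primary test at the planned evaluable number. If that is 16 per arm, it is about 67% two-sided or 78% one-sided. Which figure applies depends on settling the separate conflict over sidedness.

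The cost is one sentence removed or corrected and two figures stated. No patients are added and N stays at 40 DFU patients. The price is that the quoted power falls below 80%.

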6.1.1 Randomisation

Following written consent at -2 weeks, participants will be observed for two weeks to establish healing rate. At the end of two weeks, patients are only eligible for the intervention phase if their wound has healed <50% in the preceding two weeks. At this point, week 0, participants are allocated at random to the control or Granulox intervention group, using a randomised sequence from the freeware randomisation programme, see https://www.randomizer.org/. The randomisation is stratified for ulcer size, with PUSH score of 5 or less, and 6 or above as the cut-off. This size has been determined as the average size of a presenting foot ulcer previously (Zimny et al, 2002).

Sequential envelopes with each next randomisation allocation will be used to achieve concealment and these will be kept in the research department. The researcher will then inform the regular healthcare professional for the participant in question, and the participant themselves, which treatment they've been allocated to. The researcher will dispatch a Granulox canister to the clinic where the participant will be seen. At this stage the twice weekly treatment (though three applications per week would be allowed if dressing change is more than twice a week) will commence.

As the study involves administration of a spray it is not possible to achieve blinding for the participants nor the researchers – it is recognised that this increases the risk of bias.

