	 30 Patient will receive treatment as usual (TaU) 30 Patients will receive TaU plus adjuvant Granulox application twice weekly.
	Randomisation will be stratified for diabetes diagnosis (yes/no) and ulcer size, with cut-off PUSH score of 6 and above, or 5 or less. Patients will first go through a two week screening period; those patients with a healing rate of > 50% in 2 weeks will not be eligible for the intervention period.
Sponsor	Cumbria Partnership NHS Foundation Trust
Manufacturer & research grant provider	SASTOMED GMBH, https://granulox.de/en/sastomed contact: [name], EngelsConsult
	[name] [contact]; [contact] [contact]
Chief Investigator	[name] [name], GPwSI Research, [contact] or [name] [contact] Cumbria Partnership NHS Foundation Trust R&D Department, [name]
Co-investigators	[name] PhD, Science & Innovation Manager, [contact] or [name]; [contact] Cumbria Partnership NHS Foundation Trust R&D Department, [name]
	[name] Podiatry Lead Cumbria Partnership NHS Foundation Trust [name]
Organisation where research will take place	Cumbria Partnership NHS Foundation Trust Carleton Clinic R&D department [name]
	[contact]

Planned timeline	Recruitment start date (first patient, first visit) July 2017,
	Recruitment end date (last patient, first visit): 31 Jan 2019
	Trial end date: Apr 2019
Protocol version, date	Version 6, 10 July 2018

1.	Lay summary	6
2.	Introduction	6
3.	Investigational device	8
4.	Study hypothesis	9
4.1	Primary objective	9
4.2	Secondary objective	9
5.	Study protocol	9
5.1	Study design and timeline	9
5.2	Participant identification	10
5.3	Consent	11
5.4	Recruitment	11
5.5	Follow-up	12
5.6	Outcome measures	12
5.6.	1 Primary outcome measures	12
5.6.	2 Secondary outcome measures	12
6.	Subjects	13
6.1	Anticipated number of research subjects	13
6.1.	1 Randomisation	14
6.2	Eligibility criteria	14
6.2.	1 Inclusion criteria	14
6.2.	.2 Exclusion criteria	15
6.3	Early withdrawal of subjects	15
7.	Safety	15

7.1	Potential risks & benefits to study participants	15
7.2	Safety definitions	
7.3	Procedures for recording adverse events	
8.	Statistical consideration and data analysis plan	
8.1	Analysis of baseline characteristics	
8.2	Primary outcome statistics	
8.3	Secondary outcome statistics	.18
9. 1	Data handling and monitoring	.18
10.	Goverance of study	.19
10.1	Approvals	
10.2	Sponsor & Indemnity	19

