8.2 Primary outcome statistics

The primary objective for this trial is the healing rate of the foot ulcers, as assessed by tracing the wound using a Convatec measuring grid, or an equivalent measuring grid tool.

Confidential – This document and the information contained herein may not be reproduced, used or disclosed without written permission from Cumbria Partnership NHS Foundation Trust Page | 17

The average difference between time points will be calculated per group, 12 weeks being the primary endpoint but weeks 3, 6 and 9 will also be analysed. To compare the groups, the Mann-Whitney U-test will be applied.

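### The two-week run-in measures each ulcer's healing rate, but after the eligibility check that rate is left out of the strata, the baseline lists and the unadjusted primary test

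*Protocol*

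**What the plan says.** All references are to the protocol.

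- **Purpose of the run-in (6.1.1).** After consent at week -2, "participants will be observed for two weeks to establish healing rate". Table 3 in 5.4 schedules the grid measurement of ulcer size at both week -2 and week 0.
- **Use for eligibility.** Section 6.1.1 states that "patients are only eligible for the intervention phase if their wound has healed <50% in the preceding two weeks". The protocol summary words it as "those patients with a healing rate of > 50% in 2 weeks will not be eligible for the intervention period".
- **Prognostic evidence (Introduction).** Progress at 4 weeks is said to predict healing by 12 weeks: "If the wound has not healed by at least 50% after 4 weeks, the likelihood that the DFU will be completely healed by 12 weeks" falls to about 10%. The group of concern includes those "responding poorly to standard treatment in the first 4 weeks".
- **Stratification (summary).** "Randomisation will be stratified for diabetes diagnosis (yes/no) and ulcer size", with size split by PUSH score at 5 or less against 6 or above.
- **Primary analysis (8.2).** "To compare the groups, the Mann-Whitney U-test will be applied". No covariate is named.
- **Baseline and covariate lists (8.1, 8.3).** Neither names the change from week -2 to week 0. The Cox model in 8.3 refers back to those lists with an open-ended wording.

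**The concern.** The protocol collects a pre-randomisation measure on everyone, states that this kind of measure predicts the endpoint, and then drops it. The run-in change is measured with the same tool as the primary outcome and in the period directly before it. On the protocol's own account it is a natural candidate for the strongest baseline predictor available.

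At stake is precision. The DFU part has 20 patients per arm, 16 after the planned 20% attrition. In samples this small the arms can differ by chance in run-in healing. An unadjusted test carries that variation as noise, while an adjusted one removes the part that the run-in explains. Without the run-in change in the baseline table, a reader also cannot see whether the arms were healing alike before treatment.

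A second, smaller matter is that the run-in cut-off and the cited marker share the figure of 50% but not the time span, and no reason is given.

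**Working it through.** **1. The plan's own figure.** Table 4 gives 52% against 25%, so a difference of 27 points, with SD 30, 80% power and 5% alpha. By the normal approximation, n per arm = 2 × (z_alpha + z_beta)² × (SD/difference)².

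- One-sided: 2 × (1.645 + 0.842)² × (30/27)² = 15.3, so 16 per arm. The total is 32, and 32/0.8 = 40. This reproduces the stated 40.
- It does so on the one-tailed basis of Table 4. The text of 6.1 specifies a two-sided test, so the power figures below are two-sided.
- Completers per arm: 20 × 0.8 = 16.

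**2. Power of the planned test.** A two-sided 5% Mann-Whitney test with 16 per arm and the Table 4 inputs has about 66% power by simulation with normal outcomes. A noncentral-t approximation with efficiency 3/π gives 67%. At 20 per arm, with no attrition, the figure is about 77%.

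**3. What adjustment does.** If the run-in change correlates rho with the 12-week result, the residual SD is 30 × √(1 − rho²), which acts like multiplying the sample by 1/(1 − rho²). The power column is simulated with a rank-based ANCOVA: rank outcome and covariate over both arms together, regress one on the other, and compare the residuals between arms.

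| rho (assumed) | residual SD | sample multiplier | adjusted power, 16 per arm |
|---|---|---|---|
| 0 | 30.0 | 1.00 | about 66%, essentially no loss |
| 0.3 | 28.6 | 1.10 | about 68% |
| 0.5 | 26.0 | 1.33 | about 76% |
| 0.6 | 24.0 | 1.56 | about 82% |

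With no treatment effect the adjusted test rejected about 5% of the time, so its size is right. A repeat of the simulation agreed to within about one percentage point.

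**4. Chance imbalance.** With 20 per arm, the difference in mean run-in change has standard error √(2/20) = 0.316 SD. A difference beyond 0.5 SD in either direction therefore has probability about 11%. At rho = 0.5, a 0.5 SD imbalance moves the observed difference by 0.5 × 0.5 × 30 = 7.5 points, against a planned 27.

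**5. The cut-off beside the cited marker.** At a constant proportional rate, 50% in 4 weeks equals 1 − √0.5 = 29.3% in 2 weeks. Conversely, 50% in 2 weeks equals 1 − 0.5² = 75% in 4 weeks. On that conversion, ulcers shrinking between about 29% and 50% in the run-in pass the cut-off although they are on course to meet the 4-week marker. The two sections also treat a reduction of exactly 50% differently: 6.1.1 excludes it and the summary does not.

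**The case against.** **Stronger readings that the documents do not support.**

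- *A reader might infer that the cut-off admits fast healers who are near the ceiling by week 12 and cannot show a benefit.* At a constant rate, 40% in two weeks does project to 1 − 0.6⁶ = 95% at week 12. But that projection makes run-in rate nearly determine outcome, which does not fit correlations of 0.3 to 0.6. Suppose run-in change has mean 10-20% and SD 20-25%, truncated at 50% (assumption). A linear prediction at those correlations then puts a control ulcer that shrank 40% at about 36-55%. The Introduction's own closure figures, 24% at 12 weeks and 31% at 20, also argue against a constant rate, since a constant hazard would give 1 − 0.76^(20/12) = 37%. The share of fast healers is not given.
- *A reader might infer that the control arm must exceed the planned 25%.* Section 6.1 calls 25% an anticipated minimum and reports 37% in the pilot controls.
- *A reader might infer that the cut-off contradicts the Introduction.* The protocol never says that the cut-off derives from the 4-week marker. That marker concerns complete closure of DFUs, and 20 of the 60 patients have other ulcers. It is an unexplained mismatch.
- *A reader might infer that chance imbalance makes the planned test invalid.* It does not. The test's error rate already allows for chance imbalance under randomisation.

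**Objections that carry weight.** The gain is small at a correlation of 0.3. Run-in change and outcome share the week-0 area, so measurement error there pushes them in opposite directions and may lower the correlation. Size is already stratified by PUSH score. The rate is used once, for eligibility, and the open-ended Cox list or an unseen SAP might include it.

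These limit the size of the point. They do not remove it, because 8.2 itself names an unadjusted primary test.

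**Conclusion.** The point stands as a missed, nearly free gain in precision. It is not a flaw that invalidates the trial. The protocol measures a two-week healing rate in everyone, says early healing is prognostic, and leaves that rate out of the strata, the named baseline lists and the primary test. Adjusting for it would add about 2, 10 or 16 points of power (from about 66%) at assumed correlations of 0.3, 0.5 or 0.6, and cost essentially nothing at zero. These figures rest on the Table 4 inputs, normally distributed outcomes, a two-sided 5% test and 16 completers per arm. The documents give no value for the correlation.

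The difference between 50% in two weeks and 50% at four weeks needs an explanation. It supports no conclusion about which threshold is right.

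**What to change.** - **8.2:** state that the primary week-12 comparison is adjusted for the percentage change in grid area from week -2 to week 0, for example by rank-based ANCOVA. This keeps the rank basis of the planned test, and the stratification factors could be added to the same model. Fix the choice before outcome data are examined by arm.
- **8.1:** add the week -2 to week 0 change to the characteristics reported by arm.
- **Introduction, summary and 6.1.1:** give the reason for the two-week cut-off or reconcile it with the cited 4-week evidence, and align the wording for a reduction of exactly 50%. No alternative threshold is proposed. Changing eligibility would alter the population of a trial already recruiting.

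The cost is one line in each of 8.2 and 8.1 and a sentence of justification. Both measurements are already scheduled for every patient, so there are no new data, visits or patients.
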